### **6.4 Blinding**

This is a double-blinded study. Neither the site staff (except designated unblinded site staff if applicable) nor the subject will be informed about the product variant the subjects have been randomized to. PMPSA and CRO personnel will not be blinded to the randomization arm. Blinding process will be described in more details in the IP handling manual.

## **6.5 Investigational Product Accountability and Compliance**

### **6.5.1 Dispensing Investigational Products**

Product test at the investigational site: Product test will be performed using up to 6 P3P products(alternating between P3P-1mg and P3P-2mg). In order to continue in the study, each subject will need to test at least one product of each P3P variant during the product test. Distribution of the P3P product will be done by site staff on a product by product basis for each use. The distribution should be recorded at site logs by site staff. Used P3P consumables will be returned to the site staff at the end of each use.

Products for PK assessment and on-site use during confinement: The single P3P products used for PK assessment (second day of V2 and V6) will be provided to the subject by the site staff shortly before product use, after the product has been weighed, and will be returned to the site staff immediately after use, for after-use weighing (section 7.8.2). The products used for PK assessment will be activated (pierced) by the site staff immediately before product use.

All other products used during the confinement period will be dispensed by site staff on a product by product bases during the timeframe allowed by the protocol and will be activated by the subjects themselves.

Products for ambulatory exposure period: Starting from V2, prior to the Check-out of each visit, subjects will be provided with a sufficient number of P3P packs to cover their needs until the next visit. In the situation in which site staff judges that a re-supply is needed, optional

---

#### **Confidentiality Statement**

Data and information contained in this document are considered to constitute trade secrets and confidential commercial information, and the legal protections provided to such trade secrets and confidential information are hereby claimed under the provisions of applicable law. No part of this document may be publicly disclosed without the written consent of Philip Morris Products S.A.

---

extra visits may be accommodated. At the visits during the ambulatory period, subjects will be asked to return all used and unused P3P packs and consumables. At V6, unused products should be returned at the beginning of the visit.

#### 6.5.2 Storage and Accountability

The Investigator or designee will be responsible for the storage and accountability of P3P on site, in accordance with the Sponsor's requirements. The subject should be instructed to follow the storage and handling requirements of P3P as specified in the User guide.

The P3P components will be stored in a secured storage place at the investigational site with access limited to the authorized personnel only and according to the blinding requirements specified in the IP handling manual. Full accountability of the distributed products will be ensured by recording the timing and quantities of distributed products at each visit in appropriate logs by the designated site staff. Products used for product test, products dispensed during V2 and V6 and products used for PK will also be registered in an appropriate log.

#### 6.5.3 Investigational Products Retention

Used and unused P3P products remaining on site will be destroyed or returned to the Sponsor upon study completion and as agreed with the Sponsor.

#### 6.5.4 Compliance to Investigational Products

From Check-out at V2 until Discharge at V6, P3P product use compliance will be based on the daily self-reporting by the subjects in the product use diary (section 7.8.1). BoExp (Total NNAL and CEMA) may be used as additional tools for verifying cigarette smoking in addition to P3P use during analyses.

### 6.6 Restrictions

#### 6.6.1 Smoking and Product Use Restrictions

During the Screening period, subjects will be allowed to smoke according to their smoking habits except during the procedures of the Screening Visit (section 9.1). At Day -1 of V2, after check-in on site, smoking cigarettes and/or use any other tobacco/nicotine containing products will not be allowed. P3P use will be allowed only during the product test period.

From Day 1 until the end of the exposure period (Day 30) subjects will be instructed to exclusively use P3P. During the ambulatory visits, P3P use will be allowed except during procedures and at the discretion of the investigational site. In general, the performance of scheduled procedures has priority over the wish of a subject to use P3P. Use of cigarettes will not be allowed on site during the study visits.

#### Confidentiality Statement

Data and information contained in this document are considered to constitute trade secrets and confidential commercial information, and the legal protections provided to such trade secrets and confidential information are hereby claimed under the provisions of applicable law. No part of this document may be publicly disclosed without the written consent of Philip Morris Products S.A.

An abstinence period from any tobacco/nicotine containing products of at least 10 hours must be respected before product use for PK assessment at Day 1 and Day 30 and during the blood sampling for nicotine measurement.

During the overnight on-site visits (V2 and V6) P3P will be dispensed by the site staff on a product by product basis during the timeframe allowed by the protocol. Dispensing will be recorded in an appropriate log (section 6.5)

### 6.6.2 Dietary Restrictions

During the overnight on-site visits: V2 and V6, a standard diet will be designed for the whole confinement period. For each meal, the caloric and fat content should be controlled in order to avoid a “high-fat” diet. The FDA guidance on food-effect studies for bioequivalency testing identifies a “high-fat” diet as a diet which contains “approximately 50 percent of total caloric content of the meal [from fat] and is high in calories (approximately 800 to 1000 calories) (33).” Subjects are not allowed to bring their own food or beverages to the investigational site. Meals will be served according to the schedules provided in section 9. During these visits, consumption of water is allowed as desired. Consumption of quinine-containing drinks (e.g., tonic water) is not allowed. Subjects should be instructed to refrain from ingesting foods or beverages containing grapefruit or seville-type (bitter) oranges and marmalade within 7 days prior to the PK assessment days (Day 1 and Day 30). The same menu and meal schedule will be administered uniformly for all subjects.

There will be no dietary restrictions during the ambulatory exposure period.

Fasting state has to be observed for at least 6 hours prior to safety laboratory and biobanking blood draws at V2, V4 (safety laboratory only) and V6.

### 6.6.3 Concomitant Medication

All medication taken within 4 weeks prior to the ICF signature will be considered prior medication. All medication taken from Screening Visit to end of the Safety Follow-Up Period will be considered concomitant medication. No concomitant medication should be taken by the subjects from Screening until the end of the ambulatory exposure period without informing the Investigator or designee.

CYP2A6 is involved in nicotine metabolism. To be eligible for the study any medication with impact on CYP2A6 metabolism including, but not limited to medication listed in Table 1, must have been discontinued at least 14 days prior to Admission or for at least 5 half-lives (whichever is longer). It is at the discretion of the Investigator to assess if a termination of such medication is medically justified and safe for the subject. In addition, any medication with impact on CYP2A6 activity must be avoided at least 14 days prior to the PK assessment at Day 1 and Day 30 or for at least 5 half-lives of the drug (whichever is longer). Prior to database lock, concomitant medication will be reviewed according to their potential impact on CYP2A6 activity and assessed for their potential impact on the study results.

**Table 1 CYP2A6: Substrates, Inhibitors, and Inducers (34)**

Inhibitor	Drug Class
Amiodarone	Antiarrhythmic agent, Class III
Desipramine	Antidepressant
Isoniazid	Anti-bacterial drug
Ketoconazole	Anti-fungal medication
Letrozole	Anti-estrogen drug
Methoxsalen	Systemic psoralens
Miconazole	Anti-fungal medication
Tranylcypromine	Antidepressant
Inducer	Drug Class
Amobarbital	Barbiturate
Pentobarbital	Barbiturates
Phenobarbital	Barbiturates/anticonvulsants
Rifampin	Antimycobacterials
Secobarbital	Barbiturates
Substrate	Drug Class
Dexmedetomidine	$\alpha_2$ -Adrenoceptor, sedative
Ifosfamide	Anti-cancer, alkylating agents

Use of any other concomitant medication will be evaluated on a case by case basis by the Investigator. The Investigator is responsible for the medical care including medication of the subjects during their participation in the study. Any decisions regarding the prescription of medications will be made in the best interest of the subject. Any concomitant medications used will be fully documented (for details see section [7.3.4](#)).

## 7 STUDY PROCEDURES

Site personnel performing or recording study assessments must have the appropriate and fully documented training. An overview of all study assessments is shown in the schedule of events ([Appendix A](#)). Appropriate medical advice will be provided to the subject in case of any medical findings requiring health care. Site personnel will adhere to the site's standard operating procedures (SOPs) for study related procedures.

### 7.1 Informed Consent

Prior to any study assessment being performed, subjects will be asked to provide their written consent to participate in the study (section [1.3](#)). Study assessments must only start after the time of ICF signature by the subject.

### 7.2 Information on the Risk of Smoking, Smoking Cessation Advice and Product Debriefing

At V1, V2 and V6 all subjects will receive 1) information on the risks of smoking, 2) smoking cessation advice, and 3) debriefing on P3P.

The information on the risk of smoking and advice on smoking cessation will take the form of a brief interview according to the WHO recommendations ([35](#)). The debriefing of subjects on P3P will address any intended or unintended beliefs that participants may have about P3P. The goal of the debriefing is to help ensure that subjects enter and exit the study with an accurate understanding of the product risks, including an understanding that P3P has not currently been demonstrated to be less harmful than cigarettes.

Details of the sessions will be recorded in the source document file. This information will be given to the subjects on an individual basis during a face-to-face meeting between the subject and the Investigator or designee or may be given in a group session.

### 7.3 Clinical Assessments

#### 7.3.1 Demographic Data

Sex, date of birth and race will be recorded for each subject at V1.

#### 7.3.2 Tobacco and Nicotine Containing Products Use History and Habits

At V1, subjects will answer questions about their tobacco and nicotine containing products use history and habits. This self-reported daily consumption of cigarettes at V1 will be reviewed by the Investigator and used to assess eligibility for the study.

#### Confidentiality Statement

Data and information contained in this document are considered to constitute trade secrets and confidential commercial information, and the legal protections provided to such trade secrets and confidential information are hereby claimed under the provisions of applicable law. No part of this document may be publicly disclosed without the written consent of Philip Morris Products S.A.

At V1 and V2 the subject will also be asked if he/she is planning to quit smoking in the next 2 months i.e. before completion of the study and the answer should be documented on source documents. Only subjects not planning to quit will be considered for participation in the study.

Furthermore, subjects will be asked if they are ready to switch from cigarette smoking to use of P3P for the duration of the study. Only subjects prepared and able to comply with this requirement will be considered for participation in the study.

### 7.3.3 P3P demonstration and P3P Test

All subjects will have a demonstration of P3P (without product use) at V1.

At V2, after enrollment, and after at least 4h of abstinence from the use of any tobacco/nicotine containing products, subjects will be required to perform a product test using up to 6 P3P products (alternating between P3P-1mg and P3P-2mg). Each subject will need to test at least one product of each P3P variant during the product test. They will be instructed to use the product as described in section [6.2.1](#).

After the product test, subjects not willing and/or unable to use P3P will be discontinued from the study and will enter a 14-day Safety Follow-Up Period.

### 7.3.4 Medical History, Concomitant Disease, Previous and Concomitant Medications

Relevant medical history and any concomitant disease will be documented at V1. Medical history is defined as any condition that started and ended prior to the ICF signature at V1. A concomitant disease is defined as any condition that is either detected or is still ongoing at the time of ICF signature. The final status of any concomitant disease (i.e stop date or ongoing) should be verified at each visit.

Any medication taken within 4 weeks prior to V1 and any concomitant medication will be documented. Any medication started prior to V1 and still being taken by the subject will be considered concomitant medication. Medication initiated after V1 will also be referred to as concomitant medication. The definition of concomitant medication applies to both prescription and over-the-counter products.

Records of medication taken should include the drug name (preferably both generic and trade name), route of administration (e.g., oral, intravenous), dose and frequency (expressed in metric units, for example, mg, mL, or IU), indication, and the start and, if applicable, the stop date (day, month, and year). Therapy changes (including changes of regimen) during the study have to be documented.

### 7.3.5 Physical Examination

Physical examination will be conducted at V1, V2 (at admission and prior to discharge) and V3-V6.

#### Confidentiality Statement

Data and information contained in this document are considered to constitute trade secrets and confidential commercial information, and the legal protections provided to such trade secrets and confidential information are hereby claimed under the provisions of applicable law. No part of this document may be publicly disclosed without the written consent of Philip Morris Products S.A.

A full physical examination will include review of general appearance, skin, head, eyes, ears, nose and throat, thyroid gland, chest, lungs, back, abdomen, dentition, cardiovascular, gastrointestinal, musculoskeletal and neurological systems.

The physical examination is to be conducted by the Investigator or designated fully trained representative and assessed as normal, abnormal - not clinically significant or abnormal – clinically significant.

### 7.3.6 Body Height and Weight

Body height and weight will be recorded at V1 and BMI will be calculated using the following formula:

$$\text{BMI} = \frac{\text{weight in kilograms}}{\text{height in meters}^2} = \frac{kg}{m^2}$$

The BMI will be used to assess eligibility for enrollment.

At V2 and V6 only body weight will be recorded.

### 7.3.7 Vital Signs

Vital signs (systolic and diastolic blood pressure, respiratory rate and pulse rate) will be recorded at each visit from V1 to V6. At V2 (Day -1, Day 1 and Day 2) and V6 (Day 30) vital signs are to be checked prior to any product use and at the end of the day/at discharge.

All parameters will be recorded in supine position after subject has rested for at least 5 minutes. The subject should have abstained from smoking or using P3P for at least 15 minutes prior to measurement.

### 7.3.8 Electrocardiogram

A standard 12-lead ECG will be recorded after subject has rested for at least 10 minutes in supine position at each visit from V1 to V6. The following parameters will be documented: heart rate, PR interval, QRS interval, QT interval, and QTc interval corrected according to Bazett's formula and Fridericia's formula. Any print-outs of ECGs on thermo-sensitive paper must be photocopied and stapled together for inclusion in the source documents.

### 7.3.9 Spirometry

Spirometry will be performed in accordance with the 2005 guideline of the American Thoracic Society (ATS)/European Respiratory Society (ERS) Joint Task Force on the standardization of spirometry (36). Spirometry predicted values will be standardized to the European Community for Coal and Steel (ECCS) reference equations as published in the 1993 ERS statement (37).

#### Confidentiality Statement

Data and information contained in this document are considered to constitute trade secrets and confidential commercial information, and the legal protections provided to such trade secrets and confidential information are hereby claimed under the provisions of applicable law. No part of this document may be publicly disclosed without the written consent of Philip Morris Products S.A.

Assessed parameters will include: FEV1, FEV1 % predicted, FVC, FVC % predicted, FEF 25, FEF 25 % predicted, FEF 75, FEF75 % predicted, FEF 25-75, FEF 25-75 % predicted, FEV1/FVC. The ratio FEV1/FVC will be calculated from the highest acceptable FEV1 and the highest acceptable FVC respectively.

Spirometry without (pre-) and with (post-) bronchodilator will be performed at Screening (V1). The pre- and post-bronchodilator spirometry will be used for assessment of eligibility to the study. All post-bronchodilator spirometry testing will be performed 15-30 minutes post administration of around 400 µg of salbutamol/albuterol (usually equivalent to 4 puffs assuming 100 µg/puff). The time of salbutamol/albuterol inhalation and time of spirometry assessment will be recorded in the source document.

Spirometry without bronchodilator will be performed at V2: Day -1 before and after product test, Day 1 and Day 2 before product exposure and at the end of the daily product exposure; V3; V4; V5; V6: Day 29 at arrival on site and Day 30 prior to discharge.

All personnel performing spirometry testing should have the appropriate training and quality control measures should be put into place and be properly documented. The testing will be performed in sitting position after resting for at least 15 minutes and at least 1 hour after having stopped using cigarettes or P3P. Spirometry should be performed after assessment of vital signs and ECG.

### 7.3.10 Chest X-ray

During V1 a chest X-ray (anterior-posterior and left lateral views) will be assessed to exclude subjects with relevant pulmonary diseases. Subjects will be referred to a radiology facility for this procedure. No new examination is required if the subject can present at V1, a chest X-ray not older than 6 months with anterior-posterior and left lateral views. Available chest computed tomography (CT) or chest magnetic resonance imaging (MRI) results, or radiologist report from an equivalent radiological assessment, not older than 6 months can be accepted by Investigator for this purpose instead of chest X-ray. All reports have to be interpreted by a radiologist.

## 7.4 Biomarker Assessment

### 7.4.1 Biomarkers of Exposure to Nicotine

#### 7.4.1.1 Nicotine in plasma

For PK analysis of plasma nicotine levels, venous blood samples will be obtained at Day 1 (V2) and Day 30 (V6) according to the investigational site standard operating procedures (SOPs). A total of 11 blood samples will be taken. Three samples will be taken prior to product use (T0): 1 hour ± 5 minutes, 30 minutes ± 5 minutes and 5 minutes ± 2 minutes before T0. Thereafter in relation to T0, blood will be drawn at the following time points: after 4 minutes ± 1 minute, after 7 minutes ± 1 minute, after 10 minutes ± 1 minute, after 15 minutes ± 2

#### Confidentiality Statement

Data and information contained in this document are considered to constitute trade secrets and confidential commercial information, and the legal protections provided to such trade secrets and confidential information are hereby claimed under the provisions of applicable law. No part of this document may be publicly disclosed without the written consent of Philip Morris Products S.A.

minutes, after 30 minutes  $\pm$  2 minutes, after 1 hour  $\pm$  5 minutes, after 2 hours  $\pm$  5 minutes and after 4 hours  $\pm$  5 minutes. The actual collection time of each blood sample must be recorded on the CRF.

Since the test for nicotine concentration is highly sensitive, precautions should be taken during blood sampling and processing to prevent the contamination of samples with environmental nicotine. Detailed procedures for handling of samples are described in the separate sample handling manual (SHM)/lab manual.

#### 7.4.1.2 Nicotine Equivalents in Urine

Nicotine Equivalents (NEQ): molar sum of nicotine, cotinine, trans-3'-hydroxycotinine, nicotine-N-glucuronide, cotinine-N-glucuronide and trans-3'-hydroxycotinine-O-glucuronide will be measured in spot urine at Admission (Day -1; V2), and V3-V6. The results will be normalized to urine creatinine and expressed as concentration adjusted for creatinine.

#### 7.4.2 Other Biomarkers of Exposure in Urine

At V2-V6, total NNAL and CEMA will be measured in spot urine. The results will be normalized to creatinine and expressed as concentration adjusted to creatinine.

#### 7.4.3 Creatinine in urine

Creatinine will be measured in spot urine for normalization of urinary BoExp.

#### 7.4.4 CYP2A6 Activity

CYP2A6 activity will be assessed on Day 1 (V2) and Day 30 (V6) prior to P3P use. CYP2A6 activity drives the metabolism of nicotine to cotinine and subsequent metabolites. In this study the CYP2A6 activity will be measured in plasma using the metabolic molar ratio of *trans*-3'-hydroxycotinine/cotinine.

### 7.5 Laboratory Assessments

#### 7.5.1 Clinical Chemistry, Hematology, and Urine Analysis Safety Panel

A blood sample for hematology and clinical chemistry analysis will be taken from each subject at V1, V2, V4 and V6. Subjects should be fasting for at least 6 hours prior to sampling, except at V1 and early termination where non-fasting samples can be used. Tests will be conducted at a local laboratory ([Appendix B](#)). If during screening period a blood sample is not suitable for analysis (e.g. blood clotting) a re-test should be performed for the specific parameters which are not available. A urine sample will also be collected from each subject for urine analysis. Parameters to be tested are listed in [Table 2](#).

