**Table 2 Clinical Laboratory Parameters for Safety Panel**

Hematology	Clinical Chemistry	Urine Analysis

 
• Hematocrit
 
• Hemoglobin
 
• Mean corpuscular hemoglobin
 
• Mean corpuscular hemoglobin concentration
 
• Mean corpuscular volume
 
• Platelet count
 
• Red blood cell count
 
• White blood cell (WBC) count
 
• Differential WBC count: 
 
• Neutrophils
 
• Basophils
 
• Eosinophils
 
• Lymphocytes
 
• Monocytes
 
 
 
	
 
• Albumin
 
• Total protein
 
• Alkaline phosphatase
 
• Alanine aminotransferase
 
• Aspartate aminotransferase
 
• Blood urea nitrogen
 
• Creatinine
 
• Gamma-glutamyl transferase
 
• Fasting glucose*
 
• Lactate dehydrogenase
 
• Potassium
 
• Sodium
 
• Total bilirubin
 
• Direct bilirubin
 
• Total cholesterol
 
• Triglycerides
 
• C-reactive protein (CRP)
 
	
 
• pH
 
• Bilirubin
 
• Glucose
 
• Nitrite
 
• Red blood cell traces
 
• Protein
 
• Specific gravity
 

\* Except at Screening where non-fasting glucose can be assessed

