## 8.4 Reporting of Other Events Critical to Safety Evaluations

### 8.4.1 Abnormal Results of Laboratory Tests

Any clinical safety laboratory test result that is outside of the normal reference range will be reviewed by the Investigator and assessed for clinical significance according to its severity. The severity of abnormal laboratory test result must be assessed using CTCAE version 4.03 grading scales ([Appendix C](#)). Whenever that grading scheme is not available for the laboratory result of concern, the Investigator should assess the severity and the clinical significance of that result using his/her medical judgment.

Abnormal laboratory test results detected at the Screening Visit whose CTCAE grades are 2 or higher or still are CTCAE grade 1 and deemed clinically significant are usually concomitant disease or a manifestation of one and must be recorded accordingly.

However, in some instances, they may be assessed as AEs (and therefore must be handled according to the directions in section [8.2](#)) or as manifestations of already reported AEs. This decision will require a careful assessment of the abnormal result within the clinical context on a case-by-case basis and will depend on the Investigator's medical judgment.

Abnormal laboratory test results detected after the Screening Visit whose CTCAE grades are 2 or higher or still are CTCAE grade 1 and deemed clinically significant must be either recorded as AEs (and handled according to the directions in section [8.2](#)) or linked to a concomitant disease or still to an already reported AE.

The principles for assessing and reporting abnormal laboratory test results, emerging after the Screening Visit, using CTCAE 4.03 grading scales are set up in [Table 4](#):

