**Table 4 Principles for assessing and reporting abnormal laboratory test results**

Grading	Clinically significant?	Is it a grade increase from previous results in study?§	Report?
Grade 1	No	Not applicable	No
Grade 1	Yes	No	No*
Grade 1	Yes	Yes	Yes, as AE or linked to an already reported AE
Grade 2 or higher	No/Yes	No	No*
Grade 2 or higher	No/Yes	Yes	Yes, as AE or linked to an already reported AE

\* in this situation, this abnormal lab test result is either a manifestation of a concomitant disease or of an already reported AE.

§ grade increase in this context means the value is higher than the one from the Screening Visit.

In general, laboratory values will be recorded as “increased <lab parameter>” or “decreased <lab parameter>” to ensure consistency of recording/coding.

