12.1.4 Definitions of Baseline for Statistical Data Analysis

Baseline values for pharmacodynamic parameters (VAS Craving, Sensory Questionnaire, ABOUT™-Product experience), Product Acceptance, ABOUT™-Dependence, and Puffing/Inhalation behavior questions are defined in section 7.1, 7.2.1, 7.2.2, 7.2.3, 7.3.1, 7.5.1 and 7.3.2 respectively.

Baseline values of BoExp will be defined as the value measured on V2 (Day -1) when spot urine should be collected prior to product test. Baseline for CYP2A6 will be defined as the value determined on Day 1, see section 7.6.

For safety parameters the last assessment prior to product test at Day -1 will be considered as baseline.

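### Table 4 names two references for a laboratory grade increase, and the Screening one may be a fed sample, so an abnormal fasting triglyceride (less clearly, glucose) result after P3P use can miss AE reporting

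*Protocol*

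**What the plan says.** **Fasting state.** Protocol 7.5.1: "Subjects should be fasting for at least 6 hours prior to sampling, except at V1 and early termination where non-fasting samples can be used". Protocol 6.6.2 confirms the later visits: "Fasting state has to be observed for at least 6 hours prior to safety laboratory and biobanking blood draws at V2, V4" and V6. The footnote to Table 2 repeats the exemption for glucose: "Except at Screening where non-fasting glucose can be assessed". Fasting at Screening is thus optional, and subjects may differ in it.

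**AE rule.** For results after Screening, Protocol Table 4 reports a clinically significant Grade 1 result, or any result of Grade 2 or higher, only if there is an increase. The column heading puts the question as "Is it a grade increase from previous results in study". The footnote to that heading says "grade increase in this context means the value is higher than the one from the Screening Visit". If there is no increase the answer is `No*`, explained as: "in this situation, this abnormal lab test result is either a manifestation of a concomitant disease or of an already reported AE".

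**Pre-existing disease.** Under Protocol 8.4.1, "Abnormal laboratory test results detected at the Screening Visit whose CTCAE grades are 2 or higher", or Grade 1 and clinically significant, are usually treated as concomitant disease or a sign of one. SAP 12.5.9.4 repeats this and asks for an AE if the condition worsens after Screening.

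**Analysis baseline.** SAP 12.1.4: "For safety parameters the last assessment prior to product test at Day -1 will be considered as baseline". SAP 12.5.9.4 takes the later of the Screening and Day -1 laboratory values. When the Day -1 sample exists, the baseline is therefore that fasting sample.

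**The concern.** Triglycerides and glucose depend on meals. If the comparator is a fed sample and the later result is fasting, part or all of a real post-exposure rise can be absorbed by the meal effect in the comparator. The rule then assigns the later result to a disease that may have been entered only because the Screening sample was fed. The fasting Day -1 sample would show this, but the footnote gives it no role.

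Protocol 12.6.3 makes adverse events the main assessment of safety and plans a summary of laboratory AEs. With about 30 subjects per arm, a few reclassified events would be visible in those tables. The AE tables and the laboratory shift tables could also disagree for the same subject, because one is anchored on Screening and the other normally on Day -1.

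**Working it through.** The plan gives no figure to reproduce on this point. The check applies the Table 4 rule to illustrative values.

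**Inputs from the documents.** Table C1 triglycerides: Grade 1 is 150 to 300 mg/dL, Grade 2 is above 300 to 500. Table C1 fasting glucose: Grade 1 is above ULN to 160 mg/dL, Grade 2 is above 160 to 250.

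**Assumptions.** All subject values; a glucose ULN of 110 mg/dL; Grade 1 results taken as clinically significant; Screening fed, Day -1 and Day 30 fasting. For glucose, the fasting scale is applied to the fed Screening value for illustration only.

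**Three readings of an increase.** (a) Footnote: Day 30 value above the Screening value. (b) Day 30 grade above the Screening grade. (c) Day 30 above Day -1; value and grade give the same answer here.

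| Analyte | Screening / Day -1 / Day 30 (mg/dL) | Grades | (a) | (b) | (c) |
|---|---|---|---|---|---|
| Triglycerides | 320 / 140 / 310 | 2 / 0 / 2 | `No*` | `No*` | Yes |
| Triglycerides | 260 / 120 / 240 | 1 / 0 / 1 | `No*` | `No*` | Yes |
| Triglycerides | 320 / 140 / 330 | 2 / 0 / 2 | Yes | `No*` | Yes |
| Triglycerides | 290 / 140 / 310 | 1 / 0 / 2 | Yes | Yes | Yes |
| Glucose | 165 / 95 / 162 | 2 / 0 / 2 | `No*` | `No*` | Yes |
| Glucose | 150 / 95 / 140 | 1 / 0 / 1 | `No*` | `No*` | Yes |
| Glucose | 120 / 95 / 162 | 1 / 0 / 2 | Yes | Yes | Yes |

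**General form under the footnote.** Let F be the fasting Day -1 value, F(1+u) the fed Screening value and F(1+r) the later fasting value. If the later value is abnormal, it goes unreported whenever F(1+r) ≤ F(1+u), that is, r ≤ u.

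- First row: u = 320/140 − 1 = 1.29 and r = 310/140 − 1 = 1.21. Since r < u, the answer is `No*`.
- Third row: r = 330/140 − 1 = 1.36. Since r > u, the footnote gives Yes.
- For an assumed fed uplift of 10%, 50% or 100%, fasting rises of up to 10%, 50% or 100% can be hidden.

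**Result.** In the first row the SAP shift in severity is Normal to Moderate with a change of 310 − 140 = +170 mg/dL, while the footnote gives no AE. The third row shows that the choice between comparing values and comparing grades changes the answer even with Screening as the reference.

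**The case against.** Several points stand against a stronger statement.

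- A reader might infer that any later result of the same grade as Screening goes unreported. The footnote compares values, so a same-grade but higher value is a Yes (third row).
- A reader might infer that Table 4 rules out Day -1. The heading's reference to previous study results would include it. The firm defect is that heading and footnote disagree.
- A reader might call the bias one-way. Early termination samples may also be non-fasting, so a fed termination value set against a fasting reference can produce an AE that is only a meal effect. If Screening happened to be fasting, there is no meal effect to hide a rise.
- A reader might multiply an assumed 2% to 10% of fed Screening samples at Grade 2 by 60 subjects, giving 1.2 to 6. The documents do not supply that rate. The product would be at most the number of such subjects open to the problem, not AEs lost. Inclusion criterion 6 and exclusion criterion 3 may also remove some of them.
- Glucose is less clear. Table C1 grades fasting hyperglycemia only, so a fed Screening glucose has no proper grade and 8.4.1 leaves its severity to the investigator. The footnote's comparison of values still applies.
- There are partial safeguards. 8.4.1 says only that Screening abnormalities are usually concomitant disease and asks for case-by-case judgment. Protocol 7.3.4 and Tables 6, 9 and 10 require concomitant disease status to be checked, so an entry could be closed once a normal Day -1 result is known.

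These points limit the size. They do not remove the problem, because no passage directs the investigator to the fasting Day -1 value when applying Table 4.

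**Conclusion.** The point holds in a limited form. Table 4 is internally inconsistent about its reference. Read by its footnote, it can class a true post-exposure fasting rise as pre-existing because it compares that result with a possibly fed sample.

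Only AE classification is affected. The rise remains in the listings, the change-from-baseline summaries and the shift tables, so it would be wrong to infer that safety data are lost. The primary PK analysis is untouched.

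The number of subjects is unknown. For masking under the footnote, a subject needs all three of the following: a raised non-fasting Screening value, a lower fasting Day -1 value, and a later abnormal fasting value not above Screening. The values in the working are illustrations, not estimates. The case is clearest for triglycerides and weaker for glucose. This is a cheap improvement, not a fault that undermines the study.

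**What to change.** 1. In Table 4, make the heading and footnote name the same reference, and say whether values or grades are compared.
2. For results after first product use, set that reference to the last fasting result before the product test, at least for triglycerides and glucose. This is normally Day -1 and then matches the SAP baseline.
3. In 8.4.1, state that a non-fasting Screening triglyceride or glucose value alone is not recorded as concomitant disease until the Day -1 result is known.
4. Align the sentence in SAP 12.5.9.4 on worsening after Screening.
5. Record fasting status with each sample, so that a non-fasting early termination result can be read as such. Against a fasting reference it may look like a rise.

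The cost is a few lines of text, and a fasting-status entry if item 5 is adopted. The Day -1 fasting sample is already taken, so no visit or blood draw is added. The downside is a few more laboratory AEs to assess.
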